Because one of the most likely reasons for stopping the trial is the inability to recruit the study sample, the PI will include an assessment of recruitment futility in the annual progress report to NIDA and will consult with a biostatistician if necessary to assess the impact of significant data loss due to problems in recruitment, retention or data collection.

D. Justification of Sample Size - Using 20% as the expected response rate (RR) for the usual care group, a total sample size of 490 patients - 245 per group - are required to detect a 50% decrease in the BHI-CCM group (RR=10%) with 80% power. The total sample size amounts to an average of 7 patients in each study group within each of the 35 clinics. The sample size estimates are inflated in accordance with the cluster randomized design, incorporating the variance inflation factor $1 + (m - 1)\rho$, where m is the number of clusters ($m=35$) and ρ is the intra-cluster correlation coefficient ($\rho \leq 0.03$). Accounting for a potential 15% attrition rate, 578 total patients - 289 per group - are needed to attain the target sample size required to detect a 50% decrease in proportion of patients with average daily opioid dose ≥ 50 MEDD in the BHI-CCM group compared to the usual care group.

E. Safety Review Plan - The PI will monitor the progress of the study weekly, including reasons for attrition and whether all participants met entry criteria. Further, progress and safety will be reviewed quarterly. These progress reports will include information on recruitment, retention/attrition, and AEs and will be provided to the study investigators quarterly. The Ochsner IRB will receive a yearly report that details data relevant to the possible early termination of the study.

VI. Informed Consent: We request a waiver of consent and waiver of documentation of consent based on the requirements at 45 CFR 46.116(d).

APPENDICES

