Regulatory and financial barriers and historical separation of mental/behavioral health and primary care have created systemic barriers to effective behavioral health integration. Separate funding streams for medical and behavioral health discourage PCPs from attempting to address behavioral health issues. Health policy changes under the Medicare Access and CHIP Reauthorization Act of 2015 provides an avenue through which to incentivize behavioral health integration. Alternative Payment Models which reward quality instead of volume of care may incentivize providers through bundled payments that recognize the value of multiple providers in improving patient outcomes. The Ochsner Health Systems' Accountable Care Network is well poised to

provide critical data to health plans and health policy makers on the cost-effectiveness of the proposed multi-component intervention (See *Blue Cross Blue Shield of Louisiana* Letter of Support). One might naturally assume that care team expansion is more expensive than EMR clinical decision support. However, the decreased service utilization may justify the investment long-term. Beyond cost of care comparisons, effectiveness of the proposed intervention on quality of life, productivity, well-being and bodily pain are important considerations. We will, therefore, evaluate clinical effectiveness, cost of care and cost effectiveness of the proposed opioid management programs, using a “piggy-back” economic evaluation approach to analyze data collected during the clinical trial. (47) Refer to Section C.8.2. for details.

C.6. Aim 3: Facilitators and Barriers to Implementing Multicomponent Intervention

We will use the *Consolidated Framework for Implementation Research* to identify factors that facilitate/hinder implementation of and adherence to EMR CDS guided care and stepped opioid CCM.(48) This framework is composed of five major domains and 37 constructs: (1) *intervention characteristic* (e.g. evidence strength and quality; complexity; cost); (2) *outer setting* (e.g. patient needs and resources; external policies and mandates; peer pressure); (3) *inner setting* (e.g. implementation and learning climate; tension for change; leadership engagement; available resources); (4) *characteristics of individuals involved* (e.g. knowledge, beliefs, self-efficacy); and (5) *process of implementation* (e.g. champions; opinion leaders; planning, engaging, executing and evaluating).

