management, we will consider variable time horizon from trial duration to lifetime. We will develop a semi-Markov model to reflect the cycles of health status level of risk reduction (> 50 vs. ≤50mg MED), abstinence (discontinuation of opioids), and relapse as well as death among patients treated with opioids. (52) First, we will derive model parameters from the trial data where possible. For example, trial data will provide the transition probabilities and health utility of different health statuses. We will collect information on resource consumptions from electronic medical records which are linked with claims data. Then, we will conduct a literature review for model parameters. In addition, we will project costs and outcomes over the expected duration of treatment and its effects to ensure that all relevant differences in future outcomes of the treatment comparisons will be captured. Specifically, the cost-effectiveness analysis will use the following parameters: 1) Target population—patients on chronic opioids (long-acting or short-acting); 2) Comparators - We will compare costs for clinics with access to both the EMR CDS guided care and CHW-LCSW team versus clinics that only have access to the EMR CDS guided care; 3) Perspectives – Societal, health plans/payers, and health providers (Ochsner Health System); 4) Time horizon - 2 years, 5 years, and 10 years as well as the lifetime ; 5) Outcomes - % reduction in patient prescribed high dose (% ≤50mg MED), PEG-3 score, PROMIS-10 quality adjusted life year (QALY); 6) Cost measures - direct medical costs (inpatient, outpatient, pharmacy, lab, etc.) and program costs (material, training, staff unreimbursed time, etc.); 7) Discount rate - 3% (5% as sensitivity analysis); and 8) Results - costs and outcomes will be compared. If one program does not clearly dominate the others (lower costs and better outcomes), then we will calculate incremental cost effectiveness ratios (ICERs) using the EMR CDS guided care program as the base comparator. An incremental cost-effectiveness ratio (ICER) is defined as $\frac{\Delta_c}{\Delta_e}$, and is a comparison of costs and effectiveness between two strategies (S1 and S2), where the estimated components are defined as $\Delta_c = \text{Costs}_{S1} - \text{Costs}_{S2}$, and $\Delta_e = \text{Effectiveness}_{S1} - \text{Effectiveness}_{S2}$. The components are point estimates and have an associated uncertainty that is described by 95% confidence intervals. Primary ICER measure will be cost per % reduction below 90mg MED. Secondary measures will be cost per QALY using the PROMIS-10 or PEG-3 score. Non-parametric bootstrapping will be used to estimate parameter uncertainty (ICER 95% CI, CE scatter-plot and CE acceptability curve). Additionally, cost-effectiveness acceptability curves will be used to further interpret the results. A decision to implement the program is based on a threshold willingness-to-pay (WTP). The WTP threshold for a given healthcare system may be \$50,000 per QALY for example.(53) Therefore, programs with an ICER below \$50,000 per QALY would be desirable. We will evaluate the robustness of results with changes in model inputs, using probabilistic and one-way sensitivity analyses. Probabilistic sensitivity analysis will be executed via Monte Carlo simulation using relevant parameter distributions (e.g., population characteristics in the proposed trial). One-way analysis sensitivity analysis will test key assumptions such as 5% discounting rate, effectiveness of the additional CCM program, and key cost items (rates of inpatient stay, length of stay, and emergency room visits), as well as the WTP threshold of \$100,000 per QALY.

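### The ICER-below-threshold criterion in Protocol C.8.2 is valid only for a positive QALY difference: it reverses the decision if collaborative care is cheaper but less effective, and the bootstrap interval on the ratio fails near a zero effect

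*Protocol*

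**What the plan says.** All of the economic analysis is in Protocol C.8.2; the SAP sections supplied contain none.

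- **When a ratio is computed.** "If one program does not clearly dominate the others (lower costs and better outcomes), then we will calculate incremental cost effectiveness ratios (ICERs"). EMR CDS guided care is the base comparator, so the ratio is the cost difference over the effect difference, collaborative care minus EMR CDS.
- **Decision criterion.** "A decision to implement the program is based on a threshold willingness-to-pay (WTP"). The figure is introduced by way of illustration: "The WTP threshold for a given healthcare system may be \$50,000 per QALY for example". The text continues "Therefore, programs with an ICER below" that amount would be desirable. One-way sensitivity analysis covers other inputs "as well as the WTP threshold of" $100,000 per QALY.
- **Uncertainty.** "Non-parametric bootstrapping will be used to estimate parameter uncertainty (ICER 95% CI, CE scatter-plot and CE acceptability curve"). The cost and effect differences also get their own 95% confidence intervals, and acceptability curves are named again as an aid to interpretation.
- **Which ratio is primary.** "Primary ICER measure will be cost per % reduction below 90mg MED". Cost per QALY is secondary.

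Nothing in C.8.2 conditions the criterion on the sign of the effect difference, gives a rule for a cheaper and less effective program, mentions net benefit, or says how the acceptability curve is constructed.

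**The concern.** A ratio below a threshold means good value only when its denominator is positive. When collaborative care costs less and yields fewer QALYs, the ICER is the saving per QALY given up. A low value then means too little is saved for what is lost, and a high value is the favourable result. Read literally, the criterion endorses the first and turns down the second.

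The same feature affects the bootstrap. A replicate with cost -$500 and effect +0.01 (dominant) and one with cost +$500 and effect -0.01 (dominated) both give -$50,000. Percentiles of the ratio pool them as one result.

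Separately, a per-QALY threshold cannot be applied to a ratio whose denominator is a percentage of patients. The primary economic measure therefore has no decision criterion.

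**Working it through.** **Inputs from the documents.** Threshold λ = $50,000 per QALY, with $100,000 as sensitivity value (C.8.2); ICER = ΔC/ΔE; 245 patients per group after attrition (C.8.1), used only for the bootstrap illustration. The documents state no ICER, net benefit or interval, so there is no figure of the plan's to reproduce.

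**Inputs assumed.** The documents give no expected ΔC or ΔE and no SDs or SEs. All such values below are illustrative.

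**Step 1: algebra.** Incremental net monetary benefit is NMB = λ × ΔE - ΔC; adopt if NMB > 0.

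- If ΔE > 0, ΔC/ΔE < λ is equivalent to NMB > 0.
- If ΔE < 0, multiplying by ΔE flips the inequality, so ΔC/ΔE < λ is equivalent to NMB < 0.

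Over 1,000,000 random points at $50,000, criterion and NMB agreed at every point with ΔE > 0 and at none with ΔE < 0. At the point estimate the dominance clause removes costlier-and-worse as well as cheaper-and-better, which leaves only cheaper-and-worse exposed.

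**Step 2: worked cases in that quadrant.**

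| λ | Saving | QALYs lost | ICER | Criterion | NMB |
|---|---|---|---|---|---|
| $50,000 | $400 | 0.02 | $20,000 | desirable | 50,000 × (-0.02) + 400 = -$600 |
| $50,000 | $2,000 | 0.02 | $100,000 | not desirable | 50,000 × (-0.02) + 2,000 = +$1,000 |
| $100,000 | $8,000 | 0.1 | $80,000 | desirable | 100,000 × (-0.1) + 8,000 = -$2,000 |
| $100,000 | $12,000 | 0.1 | $120,000 | not desirable | 100,000 × (-0.1) + 12,000 = +$2,000 |

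With assumed SEs of $400 and 0.01 QALY, normal draws for the first row give P(ICER < $50,000) = 84% but P(NMB > 0) = 17%. For the second row the figures are 8% and 94%.

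**Step 3: the interval on the ratio.** Non-parametric bootstrap, 20,000 replicates, 245 per group, λ = $50,000, assumed means and SDs. The last column is the share of replicates where criterion and NMB disagree.

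| ΔC | ΔE | SD cost | SD QALY | 95% interval, ratio | 95% interval, NMB | P(ratio < λ) | P(NMB > 0) | Disagree |
|---|---|---|---|---|---|---|---|---|
| +$1,000 | +0.05 | $10,000 | 0.15 | -$16,347 to $71,825 | -$705 to $3,695 | 0.911 | 0.911 | 0% |
| +$1,000 | +0.02 | $10,000 | 0.15 | -$405,974 to $573,925 | -$2,276 to $2,217 | 0.557 | 0.494 | 7.3% |
| +$1,000 | +0.02 | $20,000 | 0.20 | -$815,535 to $880,836 | -$4,016 to $4,042 | 0.583 | 0.503 | 13.6% |
| -$1,000 | +0.01 | $20,000 | 0.20 | -$1,184,668 to $1,219,126 | -$2,522 to $5,586 | 0.728 | 0.772 | 28.8% |
| -$1,500 | -0.01 | $20,000 | 0.20 | -$1,410,283 to $1,449,966 | -$3,003 to $5,058 | 0.541 | 0.685 | 70.2% |

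In the third row, replicates fall 60.7% costlier/better, 25.8% cheaper/better, 10.0% costlier/worse and 3.6% cheaper/worse. Of the negative ratios, 28% are dominated and the rest dominant. The ratio interval works in the first row, where ΔE is clearly positive, and breaks down in the others.

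**Step 4: the primary ICER.** Both stated thresholds are in dollars per QALY. The primary ratio is in dollars per percentage reduction below 90 mg MED. No conversion or separate threshold is given, so the criterion cannot be evaluated for it. This needs no assumed effect size.

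**The case against.** The case for leaving the text alone has real substance.

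- **Existing safeguards.** Separate confidence intervals for ΔC and ΔE would show a negative or near-zero QALY difference. The scatter-plot shows the quadrants. An acceptability curve built in the usual way is P(NMB > 0) at each threshold, which is most of the remedy. This stands as mitigation. But the curve's construction is not specified, and the only written criterion is the raw ratio.
- **Status of the threshold.** The $50,000 is an example and belongs to a secondary measure. That lowers the importance, though the reversal holds whatever positive threshold is chosen.
- **Size rests on assumptions.** The 84% against 17% contrast comes from placing the assumed mean inside the failing quadrant. With ΔC = -$300 (SE $800) and ΔE = +0.01 (SE 0.01), the ratio interval is roughly -$0.69 million to +$0.63 million, yet P(ICER < $50,000) is 79.6% and P(NMB > 0) is 80.2%. The interval fails, but the decision probability hardly moves. This stands.

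Two stronger readings are tempting. One is that Hypothesis 2 is decided by this criterion. The hypothesis refers to more cost-effective care and reduced utilization and names no threshold, so the documents do not support that. The other is that the sponsor expects savings, which would make the failing quadrant likely. Protocol C.5 says only "However, the decreased service utilization may justify the investment long-term", just after allowing that team expansion might be assumed to cost more. The quadrant also needs a QALY loss, which nothing in the documents makes likely; savings with benefit is the dominance case that C.8.2 already handles.

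**Conclusion.** The point holds as a conditional defect in a written criterion and interval method.

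The reversal in the cheaper/less effective quadrant is exact and needs no data assumption. It does assume that a QALY lost is valued the same as a QALY gained. A higher price on losses would move the cut-off in that quadrant, but a low ICER there would still be the unfavourable result.

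The failure of the ratio interval depends on replicates straddling ΔE = 0. Across the assumed cases, disagreement ran from 0% of replicates with a clearly positive effect, through 7% to 29% with a small positive one, to 70% with the point estimate in the failing quadrant. The documents do not allow a choice among these. The missing criterion for the primary ICER is unconditional.

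The clinical analysis of Aim 1 is unaffected. The planned component intervals, scatter-plot and curves reduce the chance of a wrong conclusion but do not replace the stated criterion.

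**What to change.** In Protocol C.8.2, or in an economic section added to the SAP:

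1. State the decision quantity as incremental net monetary benefit, NMB = WTP × effect difference - cost difference, with adoption favoured when NMB > 0. Give bootstrap 95% CIs at $50,000 and $100,000 per QALY.
2. Define the acceptability curve as the proportion of the same bootstrap replicates with NMB > 0 at each WTP value.
3. Report the ICER as a point estimate with its quadrant. Where the effect difference is not clearly positive, omit the percentile CI on the ratio and rely on the NMB interval and the scatter-plot.
4. For the dose-based primary measure, show net benefit over a stated range of WTP per percentage point, since no threshold is given for it.

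The cost is a few sentences and one extra line of code on replicates already planned. No new data or change to the trial is needed.

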Appendix A. Patient Self-Referral through MyChart

Study teams may send recruitment notifications to potentially eligible patients via the MyOchsner patient portal. The patient-facing recruitment messages must be reviewed and approved by the IRB and then submitted in an Epic Enhancement request. The request will include the following patient-facing study name and description in Table 1.

Table 1 MyChart Recruitment Notification

Collaborative Care for Primary Care Patients with Chronic Non-Cancer Pain

Description: We are studying whether collaborative care will have a positive result on the physical, mental, and social well-being of patients living with chronic pain. Collaborative care means that your Primary Care team includes additional Behavioral Health Care professionals working together to support your care plan. The Behavioral Health Care team member's services (e.g. care coordination, counseling, medication management) are free for a limited time. To make services easier to use, you may meet with your behavioral health care team by telephone or virtual visits through MyOchsner.

We would like to speak with you to determine if you are eligible. If you are, we will follow-up with your Ochsner primary care provider to refer you to participate.

This study is funded by the National Institute of Health, grant number 1 R01 DA045029-0. This message has been approved by the Ochsner Institutional Review Board, Protocol # 2018.294

Name | Title | Ochsner Center for Outcomes and Health Services Research | [contact]

Once the request is approved, the study team builds a report based on patient eligibility in Epic Reporting Workbench or other Epic platform recommended by Ochsner IS. The report criteria may include:

- Age in years: greater or equal to 18
- Study: (Display)
- Enrollment Status Type: (Display this column, so we don't send to someone already screened)
- Mychart status: Active
- Patient Status: Not equal to Deceased
- Most recent questionnaire answers (PHQ4): (Display if available, as to not repeat screenings completed within the last month)
- Diagnosis: exclude serious mental illness

The generated report can be used to “Send Recruitment Request” to patients on the report. The Recruitment Studies Notice shown below in Figure 1, shows up on the homepage of the patient’s MyOchsner account.

Figure 1 Recruitment Studies Notice

[figure not shown]
Join research studies for which you are a good candidate. You have a new study to review.

Patients or proxy account users (family/friends/caregivers) may click on the notice to be taken to the Research Studies/Available Studies page to review the study’s recruitment message. Patients will be able to select “I’m Interested” or “No Thank You” to whether they would like to notify the study team that they may want to participate. The responses, both positive and negative, are populated in the study coordinator and principal investigator’s Epic InBasket, in the system’s pre-labeled **Research Recruitment** folder.

Interested Patients Workflow

1. The study coordinator will review the Research Recruitment folder for patients with “**Completed**” enrollment status. “Completed” is the default enrollment status based on the recruitment notice being read and “**I’m Interested**” being selected by the patient. **If the patient has not responded to the notice**, the default enrollment status is “**Identified**”. Figure 2 is an image of the of Enrollment Status Categories in Epic.

Figure 2 Epic Enrollment Status Categories

2. The CHW or study team member will conduct a **brief chart review** to look for anything in the chart that would deter or defer patients from following up (e.g. admission, prolonged/terminal illness).
3. If no concerns, or red flags, the CHW or study team members (i.e. only Ochsner employees or Ochsner medical students) will call the patient to explain the program and invite them to complete the screening assessment with the PHQ9 and GAD7. If the patient screens eligible and is agreeable, the CHW or study team member will complete the intake procedures (PROMIS and scheduling appointment with the LCSW). Patients may have the option to

complete screening and/or intake by phone or if available, in-person (e.g. upcoming clinic appointment).

4. When **the study team/CHW-administered PHQ9/GAD7 score meets the threshold (either score ≥ 10)**, the PCP will be notified of their patient's program eligibility or ineligibility and will be given instructions on how to place the referral mentioned above.

Screening Log

The study team will add all patients screened for eligibility to the Research Study activity in Epic and document the screening date (i.e. start date), the recruiter name (i.e. CHW), the reason for ineligibility or decline, and enrollment status (e.g. enrolled, screen failed, ineligible-did not meet full criteria, declined).

# STATISTICAL ANALYSIS PLAN

## 1. Introduction

**1.1 Study Design:** Type II effectiveness-implementation hybrid stepped wedged cluster randomized trial

## 1.2 Main Study Outcomes

### 1.3 Primary

**1.3.1** Odds Ratio of average morphine equivalent daily dose (MEDD) of opioid prescription  $\geq 50$  mg between study groups

### 1.4 Secondary

#### 1.4.1 Comparison of study groups

- Rate Ratio for average MEDD in post-index versus pre-index periods
- Inpatient hospital admission per 1000 patients
- Emergency Department visits per 1000 patients
- Odds Ratio for new post-index documented pain agreement
- Odds Ratio for new post-index documented urine drug screening
- Odds Ratio for new post-index documented naloxone prescription order
- Odds Ratio for new post-index documented referral to non-mental/non-behavioral health specialist
- Odds Ratio for new post-index documented anti-depression medications

#### 1.4.2 Among patients in the collaborative care intervention group

- Proportion with improvements in symptoms of depression (PHQ-9)
- Proportion with improvements in symptoms of anxiety (GAD-7)
- Change in average rating of quality of life (PROMIS-10)
- Change in average rating of pain (PEG-3)
- Change in average rating of opioid misuse (COMM-9)

**2. Main Objective:** Compare the clinical effectiveness of electronic medical record clinical decision support [EMR CDS] versus additional integrated behavioral health collaborative care management

- a. **Hypothesis 1:** higher proportion of patients who receive additional collaborative care compared to EMR-CDS only will have greater decreases in the rate of high-dose opioid prescriptions; higher rates of receiving opioid risk mitigation care (e.g. urine drug screens, naloxone, functional assessments specialty care); and greater reductions in inpatient hospitalizations and/or emergency department utilization.

